| Monthly frequency measurements (including migraine days, headache days, migraine attacks, acute headache medication treatment days, acute migraine-specific medication treatment days)If diary days in entire baseline or interval post baseline >=14 (including retrospective eDiary days), then do proration; Else monthly measurement is set to missingNumber of observed migraine days * 28/ Number of information days in intervalIf diary days migraine days, headache days, migraine attacks, acute headache medication treatment days, acuteIf diary days baseline or interval post baseline >=14 (including retrospective eDiary days), then do proration;Number of information days in interval adays in intervalImage: the set to missingElse monthly measurement is set to missingImage: the set to missing | Monthly Endpoint | Condition | Proration Method (does not need to be rounded) |
|--|---|---|---|
| | Monthly frequency measurements (including migraine days, headache days, migraine attacks, acute headache medication treatment days, acute migraine-specific medication treatment days) | If diary days in entire baseline or interval post baseline >=14 (including retrospective eDiary days), then do proration; Else monthly measurement is set to missing | Number of observed migraine days * 28/ Number of information days in interval [information day is a diary day or headache day] |
| [diary days is a day with all headache related questions completed retrospectively or not] | | [diary days is a day with all headache related questions completed retrospectively or not] | |

Missing PROs (HIT-6) scheduled to be collected at office visit at certain assessment will not be imputed.

5.1.5.2 Missing Baseline Evaluation

Missing baseline evaluations will not be imputed.

All subjects included in the full analysis set will have baseline monthly rate or monthly average of migraine and non-migraine headaches related measurements after applying proration rule defined in Section 5.1.5.1 since only subject with $\geq 80\%$ compliance of eDiary use during baseline will be eligible for randomization.

5.1.5.3 Missing Post-baseline Evaluation in Double-Blind Treatment Period

Primary analysis of continuous efficacy endpoints during the 12-week randomized DBTP will be conducted using the linear mixed effects repeated measures model on observed data without imputation (see Section 5.4.1).

In the sensitivity analysis on primary and secondary efficacy endpoints during the 12-week DBTP, missing continuous efficacy endpoints will be handled using baseline observation carried forward (BOCF) method, and multiple imputation (MI) with assumption of missing at random (MAR) and missing not at random (MNAR) (with control-based pattern imputation and treatment effect adjusted imputation), respectively. See below for more details.

In BOCF method, post-baseline missing continuous efficacy endpoints during double-blind treatment phase will be imputed using the baseline observed value. For example, if subject has all of the post-baseline values as missing, then all of the post-baseline values will be imputed using the observed baseline value.

In non-responder imputation (NRI) method, post-baseline missing dichotomous secondary

efficacy endpoints (responder [Yes/No] based on \geq 50%, \geq 75% and 100% reduction from baseline in monthly migraine days,

, achievement of at least a 5-point reduction from baseline in HIT-6 total score) during double-blind treatment phase will be imputed as non-responder at each corresponding time point.

To address the impact of missing data on primary efficacy analysis, the amount of missing data, the distribution of missing data among treatment groups, and the reasons for missing data will be examined.

If the proportion of missing data in primary endpoint is high (e.g., > 20% for primary analysis at week 12) or if imbalance occurs amongst the treatment groups, further analysis will be performed to

- examine the frequency and reason of missing data
- determine if there are any patterns in the missing data

| Novartis | For business use only | Page 53 |
|-----------------|-----------------------|--------------|
| SAP Amendment 1 | | CAMG334A2302 |

• distinguish true missing values from other unknown values (e.g., due to measurement or sample processing error)

Additional sensitivity analyses, including those based on alternative missing data assumptions, will be performed as deemed appropriate and necessary.

5.1.5.3.1 Multiple Imputation (MI) and MCMC Method

The multiple imputation assume that the missing data are missing at random (MAR), that is, the probability that an observation is missing may depend on the observed values but not the missing values. It also assumes that the parameters q of the data model and the parameters f of the missing data indicators are distinct. That is, knowing the values of q does not provide any additional information about f, and vice versa. If both MAR and the distinctness assumptions are satisfied, the missing data mechanism is said to be ignorable. The MI procedure provides three methods for imputing missing values and the method of choice depends on the type of missing data pattern. For monotone missing data patterns, either a parametric regression method that assumes multivariate normality or a nonparametric method that uses propensity scores is appropriate. For an arbitrary missing data pattern, a Markov chain Monte Carlo (MCMC) method that assumes multivariate normality can be used.

In MCMC, one constructs a Markov chain long enough for the distribution of the elements to stabilize to a common, stationary distribution. By repeatedly simulating steps of the chain, it simulates draws from the distribution of interest.

In Bayesian inference, information about unknown parameters is expressed in the form of a posterior distribution. MCMC has been applied as a method for exploring posterior distributions in Bayesian inference. That is, through MCMC, one can simulate the entire joint distribution of the unknown quantities and obtain simulation-based estimates of posterior parameters that are of interest.

Assuming that the data are from a multivariate normal distribution, data augmentation is applied to Bayesian inference with missing data by repeating a series of imputation and posterior steps. These two steps are iterated long enough for the results to be reliable for a multiply imputed data set (Schafer 1997). The goal is to have the iterations converge to their stationary distribution and then to simulate an approximately independent draw of the missing values. Sample SAS code for MI using MCMC method will be provided as instruction to TFLs.

Further, as a sensitivity analysis, the pattern-mixture model approach is used to model the distribution of a response as the mixture of a distribution of the observed responses and a distribution of the missing responses, for which the missing values can be imputed under a plausible scenario for which the missing data are missing not at random. The control-based pattern imputation, in which, the set of observations from control group are used to derive the imputation model.

5.1.5.3.2 Multiple imputation sensitivity analyses steps

The following steps are followed, in order to create the structure of the analysis dataset where missing values and appropriate variables could be imputed.

- Obtain subject id, treatment group (trt01pn), stratification factor (prior migraine prophylactic treatment failed, a dichotomous variable), sex, race group, age group, BMI group, disease duration at baseline from ADBS or ADSL.
- Obtain avisitn paramed param aval avale base chg dtype from ADATTACK
- Perform minor data manipulation, as required, to reinstate the missing data, eg if dtype="LOCF" then aval=., avalc=""" and chg=..
- Ensure the baseline values are included in the chg variables before data transformation, e.g. if avisitn=2000 then chg=base.
- Transpose all the data so you have one observation per subject and each visit becomes a variable within its own right, e.g. rows where avisitn=2004, 2008, 2012 become the column wk4, wk8, wk12.
- Impute the missing data for MAR and MNAR separately according to the methods in next steps

MAR multiple imputations steps:

Note that some variables (for ex., duration of migraine) might have missing values and there is a mix of categorical and continuous variables in the modelling of the missing data. Therefore, fully conditional specification (FCS) methods are employed within proc mi to impute the missing data.

- FCS logistic is used for dichotomous variables; discrim is used for categorical variables with more than 2 categories; regpmm is used for continuous variables.
- wk0, wk4, wk8 and wk12 represent the chg variable for each of the visits respectively, where wk0 is baseline.

MNAR multiple imputations steps:

- Here is an implementation of the pattern-mixture model approach that uses a controlbased pattern imputation and imputing the missing data step-by-step, where the baseline variables inform on any missing baseline efficacy values. The baseline efficacy values then inform on the next visit, which then informs on the next visit and so on until all visits have non-missing data.
- Furthermore, an option is used at post-baseline visits (modelobs= (trt01p='Placebo')) to include an adjustment for the fact that any missing data from active treatment subjects will be similar to placebo subjects under the assumption that missing values in the active treatment subjects implies they are no longer on treatment. That is, an imputation model for the missing data in the active treatment group is constructed not from the observed data in the active treatment group but rather from the observed data in the placebo group. This model is also the imputation model that is used to impute missing data in the placebo group.

MAR and MNAR modeling step:

For the change from baseline in MMD analysis, it uses a linear mixed effects repeated measures model on imputing data under the assumption of MAR or MNAR. There is no gaps in imputed data, therefore, all the data is available to analyze and can use a fixed effects model looking only at the avisitn=2012/week12 data.

MAR and MNAR combining step:

• The output dataset with the treatment LS means (LSMEANS) and the treatment differences (DIFF) are then sorted, manipulated and read into proc mianalyze to

combine the individual sets of imputed results into one set of overall results, see all steps SAS codes in TFLs document.

5.2 AEs coding/grading

Adverse events are coded using the Medical dictionary for regulatory activities (MedDRA) terminology.

Adverse event severity is graded based on NCI Common Toxicity Criteria version 4 or higher, which is available at the following: http://evs.nci.nih.gov/ftp1/CTCAE/CTCAE_4.03_2010-06-14_QuickReference_5x7.pdf

The CTCAE displays Grades 1 through 5 with unique clinical descriptions of severity for each AE based on this general guideline:

Grade 1 - Mild; asymptomatic or mild symptoms; clinical or diagnostic observations only; intervention not indicated.

Grade 2 - Moderate; minimal, local or noninvasive intervention indicated;

Grade 3 - Severe or medically significant but not immediately life-threatening; hospitalization or prolongation of hospitalization indicated; disabling;

Grade 4 - Life-threatening consequences; urgent intervention indicated.

Grade 5 – Death related to AE.

5.3 Laboratory parameters derivations

CTCAE grading for the laboratory toxicity will be derived based on NCI Common Toxicity Criteria version 4 or higher, which is available at the following: http://evs.nci.nih.gov/ftp1/CTCAE/CTCAE_4.03_2010-06-14_QuickReference_5x7.pdf

5.4 Statistical models

5.4.1 **Primary analysis**

The primary endpoints of the study will be first tested for each of AMG 334 70 mg and 140 mg compared to placebo, respectively.

- Null Hypothesis: In subject with episodic migraine, the AMG 334 treatment group is the same as placebo, in terms of the reduction from baseline in mean monthly migraine days in the last month (month 3) of the DBTP
- Alternative Hypothesis : In subject with episodic migraine, the AMG 334 treatment group is different from placebo, in terms of the reduction from baseline in mean monthly migraine days in the last month (month 3) of the DBTP

It will be analyzed using a linear mixed effects repeated measures model with treatment group, baseline value, stratification factor, scheduled visit, and the interaction of treatment group with scheduled visit. In repeated statement, an unstructured covariance matrix will be used.

5.4.2 Secondary analysis

5.4.2.1 Method I

The first secondary analyses will compare the 50% response rate, which is defined as the proportion of patients who achieve at least a 50% reduction from baseline in monthly migraine days in the last month (month 3) of the Double-Blind Treatment Period, for each of AMG 334 70 mg and 140 mg compared to placebo, respectively.

- Null Hypothesis: In subject with episodic migraine, the AMG 334 treatment group is inferior or the same as placebo, in terms of the proportion of patients who achieve at least a 50% reduction from baseline in monthly migraine days in the last month (month 3) of the Double-Blind Treatment Period
- Alternative Hypothesis : In subject with episodic migraine, the AMG 334 treatment group is superior to placebo, in terms of the proportion of patients who achieve at least a 50% reduction from baseline in monthly migraine days in the last month (month 3) of the Double-Blind Treatment Period

More precisely, the null hypothesis stating that the odds ratio between the two treatment arms less than or equal to 1 will be tested against the one-sided alternative.

H₀:
$$\theta_1 \leq 1$$
 vs H₁: $\theta_1 > 1$

where θ_1 is the odds ratio of active over corresponding placebo.

Test statistic:

After the missing data are imputed as non-response, a Cochran-Mantel-Haenszel (CMH) test stratified by the randomization strata will be used under a significance level of alpha/2, one-sided (alpha, two-sided; See further details in protocol Section 9.5 and Section 2.6.2 of this document for the value of alpha) to evaluate the association between the 50% responder rate and the treatment. The estimated common odds ratio, confidence intervals and p-values will be reported.

Sensitivity analysis:

• Logistic regression analysis will be used to test the superiority of AMG334 arm in the 50% response rate after the missing data are imputed as non-response. Baseline migraine days will be used as a covariate along with treatment and stratification factor as fixed effects in the model.

The odds ratio of treatment group compared to placebo group with associated 95% confidence intervals and 2-sided p-values will be provided.

5.4.2.2 Method II

The secondary continuous endpoints of the study will be first tested for each of AMG 334 70 mg and 140 mg compared to placebo, respectively.

- Null Hypothesis: In subject with episodic migraine, the AMG 334 treatment group is same as placebo, in terms of the reduction from baseline in the continuous endpoint of interest in the last month (month 3) of the DBTP
- Alternative Hypothesis : In subject with episodic migraine, the AMG 334 treatment group is different from placebo, in terms of the reduction from baseline in the continuous endpoint of interest days in the last month (month 3) of the DBTP

It will be analyzed using a linear mixed effects repeated measure model with treatment group, baseline value, stratification factor, scheduled visit, and the interaction of treatment group with scheduled visit. In repeated statement an unstructured covariance matrix will be used.

5.4.3 Van Elteren Test for Continuous Response Variable with Strata

When assumption of normality in analysis of covariance model is violated, then a Van Elteren's test for stratified continuous data can be used. Van Elteren's test is a nonparametric test that compares treatments in the presence of blocking. The test is an extension of Wilcoxon's rank-sum test (Van Elteren 1960).

Van Elteren proposed to combine stratum-specific Wilcoxon rank-sum statistics with weights inversely proportional to stratum size.

Suppose that the data obtained for the subjects in two treatment groups are split into J strata. Then, the stratified Wilcoxon test statistic is

$$W^{*} = \frac{\sum_{j=1}^{J} a_{j}(T_{j} - E(T_{j}))}{\sqrt{\sum_{j=1}^{J} a_{j}^{2} Var(T_{j})}}$$

where j=1,..,J denote the strata, $(T_j - E(T_j))$ and $\sqrt{Var(T_j)}$ are the numerator and denominator respectively of the Wilcoxon statistic for the data in strata *j* and *a*_j is the weight applied to each strata. The test statistic can be rewritten in the form

$$W^* = \frac{\sum_{j=1}^{J} a_j \sqrt{\frac{n_{0j} n_{1j}}{n_{0j} + n_{1j}}} \left(\frac{1}{n_{0j}} \sum_{k=1}^{n_{0j}} R_{0jk} - \frac{1}{n_{1j}} \sum_{k=1}^{n_{1j}} R_{1jk}\right)}{\sqrt{\sum_{j=1}^{J} a_j^2 \frac{1}{n_{0j} + n_{1j} - 1} \sum_{i=0}^{1} \sum_{k=1}^{n_{ij}} (R_{ijk} - \overline{R}_{\bullet j \bullet})^2}}$$

where R_{ijk} is the rank of the observation X_{ijk} within strata j, i=0,1 denotes the treatment group, j=1,...,J denotes the strata, $k=1,...,n_{ij}$ denotes the subjects within the i^{th} treatment group in the j^{th} strata and $\overline{R}_{\bullet j\bullet}$ is the average rank of all observations in strata j. This form of the test statistic was programmed into the SAS macro used for analyses.

Assuming no ties within the data, the simplified form of the variance, that is

$$\left[\sum_{j=1}^{J} a_{j}^{2} \frac{1}{12} \cdot n_{0j} n_{1j} (n_{0j} + n_{1j} + 1)\right]$$

can be used.

Two weights have been used to combine results over strata:

"Locally best":
$$a_j = \sqrt{\frac{n_{0j}n_{1j}}{n_{0j} + n_{1j}}} \cdot \frac{1}{n_{0j} + n_{1j} + 1}$$

"Type II" (used for pooled analyses): $a_j = \sqrt{\frac{n_{0j}n_{1j}}{n_{0j} + n_{1j}}}$.

For large sample sizes (within each strata) the test statistic has a standard normal distribution; therefore the two-sided test would reject the null hypothesis if $|W^*| > u_{\alpha/2}$.

The test can easily be implemented using the SAS, PROC FREQ. The FREQ procedure is used with the TABLE statement options CMH2 and SCORES=MODRIDIT. The second CMH statistic, labeled "Row Mean Scores Differ" is the asymptotic test statistic.

As shown by Koch et al 1982, the Van Elteren test is a member of a general family of Mantel-Haenszel mean score tests. For more information about the Van Elteren test and related testing procedure, refer to Lehmann 1975, Koch et al 1990.

5.5 Rule of exclusion criteria of analysis sets

The protocol deviations resulting in participants' exclusion from analysis sets are defined below (Table 5-2). A complete list of the PDs can be found in the Edit Check Specifications document in CREDI.

| Table 5-1 Deviation Codes Description | |
|---|--|
|---|--|

| Deviation code | Text description | Deviation ID |
|----------------|--|-----------------|
| 1 | SELECTION CRITERIA NOT MET | INCLXX ; EXCLXX |
| 2 | PATIENT NOT WITHDRAWN AS PER PROTOCOL | WITHXX |
| 3 | PROHIBITED CONCOMITANT MEDICATION | COMDXX |
| 4 | TREATMENT DEVIATION | TRTXX |
| 998 | OTHER | OTHXX |

| Table 5-2 | Subject Classification | |
|--------------|--|---|
| Analysis Set | PD ID that cause subjects to be excluded | Non-PD criteria that cause subjects to be excluded |
| RAS | NA | Not randomized |
| FAS | NA | Not randomized |
| | | Not in the randomized set; |
| | | No double-blind study drug taken; |
| | | No change from baseline measurement in monthly migraine day during the DBTP |
| SAF | NA | No double-blind study drug taken |
| | | |

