#### 9.1 Analysis sets

The All Randomized Set (ARS) includes all subjects who were randomized in the study. Subjects will be analyzed according to their randomized treatment, regardless of the treatment received. Tabulations of demographic and baseline characteristics, disposition, and important protocol deviations (IPD) will utilize this analysis set.

The Full analysis set (FAS), which is a subset of ARS, will consist of all participants who started study medication and have completed at least one post-baseline efficacy measurement during the DBTP. In FAS, subjects will be analyzed according to randomized treatment, regardless of the actual treatment received.

The Safety analysis set (SAF) will consist of all randomized subjects who received at least one dose of investigational product and will be analyzed based on actual treatment received.

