2.2 Analysis sets

The Randomized analysis Set (RAS) includes all subjects who were randomized in the study. Subjects will be analyzed according to their randomized treatment, regardless of the treatment received. Tabulations of demographic and baseline characteristics, disposition, and important protocol deviations (PD) will utilize this analysis set.

The Full analysis set (FAS), which is a subset of RAS, will consist of all participants who started study medication and have completed at least one post-baseline efficacy measurement during the DBTP. In FAS, subjects will be analyzed according to randomized treatment, regardless of the actual treatment received.

The Safety analysis set (SAF) will consist of all randomized subjects who received at least one dose of investigational product and will be analyzed based on actual treatment received.

As a general rule, the actual treatment is the randomized treatment. Only in case a patient received an incorrect dose at all the visits (up to DBTP completion or discontinuation), the actual treatment is the one received.

Rule of exclusion criteria of analysis sets is presented in Appendix 5.5.

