2.5 Analysis of the primary objective

2.5.1 **Primary endpoint**

The primary efficacy variable is the change from baseline in monthly migraine days in the last month (Month 3) of the DBTP.

Analysis of the primary endpoint will utilize the FAS. Subjects will be analyzed according to their randomized treatment group regardless of the actual treatment received during the study.

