2.5.4 Sensitivity analyses

Analysis of the primary efficacy variable at week 12 will be repeated using an analysis of covariance (ANCOVA) model including treatment group and stratification factor as fixed effects in the model with baseline value as covariate.

Missing data at Week 12 will be imputed using its baseline value (baseline observations carried forward BOCF). In addition, multiple imputation (MI) techniques applying missing at random (MAR) and missing not at random (MNAR) approaches will be used to assess the impact of

| | Page 34 |
|-----------------|--------------|
| SAP Amendment 1 | CAMG334A2302 |

missing values on the interpretation of the results during the DBTP (the imputation methods are described in Section 5.1.5.3).

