2.6.2 Statistical hypothesis, model, and method of analysis

Analysis of secondary efficacy endpoints will utilize the FAS except for the analysis of change from baseline in monthly acute migraine-specific treatment days in Month 3 of the DBTP, which will be conducted based on the subgroup of patients who used acute migraine-specific medication during baseline. Subjects will be analyzed according to their randomized treatment group regardless of the actual treatment received during the study.

The above continuous change from baseline efficacy endpoints will be analyzed using a linear mixed effects repeated measures model with treatment group, baseline value, stratification factor, scheduled visit, and the interaction of treatment group with scheduled visit, without any imputation for missing data. If applicable, in the repeated statement, an unstructured covariance matrix will be used.

The dichotomous endpoint (Proportion of patients who achieve at least a 50% reduction from baseline in monthly migraine days in the last month of DBTP) will be analyzed based on Cochran-Mantel-Haenszel (CMH) test after patients who have missing monthly migraine day data at Month 3 of the DBTP imputed as non-responders.

The description of the models can be found in Section 5.4.

In all cases, estimates (difference or odds ratio) of treatment group compared to placebo group with associated nominal 95% confidence intervals and nominal two-sided p-values will be provided.

A hierarchical gate-keeping procedure and the Hochberg method will be used to maintain the overall 2-sided study-wise type I error rate at 0.05 for the primary endpoint and secondary efficacy endpoints. The primary endpoint, the change from baseline in monthly migraine days

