2.6.4 Sensitivity analyses

In order to assess the robustness of the analysis for the secondary endpoint "Proportion of patients who achieve at least a 50% reduction from baseline in monthly migraine days in the last month of DBTP (Month 3)", next analysis will be done:

• Logistic regression analysis will be used to get odds ratio of each AMG 334 group vs placebo in the 50% response rate after the missing data are imputed as non-response.

In all cases, the odds ratio of each treatment group compared to placebo group with associated 95% confidence intervals and p-values will be provided.

Detailed secondary efficacy analysis methods, sensitivity analyses, and covariates included in the models are summarized in the table below.

Table 2-4 Summary of secondary efficacy Endpoints and Analysis Methods during DBTP

| Endpoint | Primary Summary and Analysis Method | Sensitivity Analysis |
|----------|--|----------------------|
|----------|--|----------------------|

| The achievement of at least a 50% reduction from baseline in monthly migraine days in the last month of the double-blind period | Analysis Method I: 1. Summary statistics by visit using observed data 2. A stratified Cochran- Mantel-Haenszel (CMH) test will be used after the missing data are imputed as non-response | Analysis method III , NRI: analyze using a logistic regression model that includes treatment and stratification factor as fixed effects and baseline monthly migraine days as covariate |
|--|---|--|
| Change from baseline in monthly acute migraine- specific medication treatment days in the last month of the double-blind period | Analysis method II: 1. Summary statistics by visit using observed data 2. Least squares mean at each time point calculated based on a linear mixed effects repeated measures model including treatment group, baseline value, stratification factor, scheduled visit, and the interaction of treatment group with scheduled visit using observed data. In repeated statement, an unstructured covariance matrix structure will be used. 3. Test pairwise treatment difference (each AMG 334 dose group vs placebo), using a contrast from the model above. | N.A. |
| Change from baseline in headache impact scores as measured by the HIT-6 in the last month of the double- blind period | Analysis method II. | N.A. |

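### SAP Table 5-2 defines a narrower FAS than SAP 2.2, and on that FAS the missing-data analyses omit the dosed patients with least migraine-day data

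*SAP*

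**What the plan says.** **Who is in the FAS.** SAP 2.2 defines the set as "all participants who started study medication and have completed at least one post-baseline efficacy measurement during the DBTP". Protocol 9.1 has the same condition: "have completed at least one post-baseline efficacy measurement during the DBTP". Neither names the endpoint. SAP 2.2 then refers to Appendix 5.5, where Table 5-2 lists among the grounds for exclusion "No change from baseline measurement in monthly migraine day during the DBTP".

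**When a migraine-day value is missing.** SAP 5.1.5.1 sets every monthly diary measure to missing if the month has fewer than 14 eDiary days. SAP 2.1.1.3 makes the change missing if either the baseline or the later value is missing.

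**How missing values are handled.** For the primary variable SAP 2.5.4 says "Missing data at Week 12 will be imputed using its baseline value", and adds multiple imputation under MAR and under a control-based MNAR model. SAP 5.1.5.3 gives as its BOCF example: "if subject has all of the post-baseline values as missing, then all of the post-baseline values will be imputed using the observed baseline value". The 50% responder endpoint counts a missing Month 3 as non-response.

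**Which set is used.** SAP 2.5.1: "Analysis of the primary endpoint will utilize the FAS". SAP 2.6.2: "Analysis of secondary efficacy endpoints will utilize the FAS", with an exception only for medication days. SAP 2.5.4 and 5.1.5.3 name no set for BOCF or multiple imputation.

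**The concern.** The two FAS wordings differ for a real type of patient. HIT-6 is a secondary efficacy variable collected at visits, so a dosed patient can have a HIT-6 score after baseline and no evaluable diary month.

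The second issue matters more. BOCF, control-based imputation and non-responder imputation are there to test or penalise missing data. If they run on the Table 5-2 FAS, the dosed patients with least data are removed before the penalty is applied. Whether a patient is removed depends on behaviour after randomisation, so the loss need not be equal across arms. The responder endpoint is also part of the type I error control.

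**Working it through.** **1. The two rules side by side.** Take a dosed patient with a baseline value. Migraine days at Weeks 4, 8 and 12 can each be observed or missing, and post-baseline HIT-6 can be observed or missing: 2³ × 2 = 16 patterns.

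- SAP 2.2 admits every pattern except the one with nothing observed: 15.
- Table 5-2 admits the 7 migraine-day patterns with at least one value, with or without HIT-6: 7 × 2 = 14.
- The pattern that separates them is migraine days missing in all three months with HIT-6 observed.
- All-missing migraine-day patterns inside the FAS: 1 under SAP 2.2, 0 under Table 5-2.
- Patterns admitted by Table 5-2 with Week 12 missing but an earlier month observed: 3 × 2 = 6. BOCF applies to these as intended.

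**2. Do the other endpoints give the BOCF example a use?** Medication days fall under the same 14-day diary rule, so a patient with no evaluable month has no value there either. For HIT-6, SAP 5.1.5.1 says missing values are not imputed. Table 2-4 lists the sensitivity analysis as N.A. for both continuous secondary endpoints, although SAP 5.1.5.3 mentions secondary endpoints in general.

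**3. How many patients?** The documents give no count, so the rates are assumptions tied to their figures. Diary recording continues after treatment stops (Protocol 5.6.2), so exclusion mostly means leaving the study within about 2 of the 12 weeks. With steady loss that is one sixth of all loss.

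- About 95% retention at three months on active treatment (Protocol 3.6), applied here to placebo too: 5% / 6 = 0.83%.
- Planned drop-out of 10% (Protocol 9.8): 10% / 6 = 1.67%.
- 140 mg, 220 patients: 220 × 0.0083 = 1.8 to 220 × 0.0167 = 3.7.
- Placebo, 330 patients: 330 × 0.0083 = 2.8 to 330 × 0.0167 = 5.5.

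**4. Effect on the estimates.** Let eA and eP be the excluded shares on active and placebo.

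- Responders, 140 mg vs placebo, with assumed FAS rates of 45% and 30% (difference 15.0 points): 0.45(1 − eA) − 0.30(1 − eP).
- BOCF, 70 mg vs placebo, with changes of −2.9 and −1.8 days (Protocol 1.1, study 20120297; difference −1.10): −2.9(1 − eA) + 1.8(1 − eP).
- Borderline case: the 140 mg rate is set so that the pooled two-proportion test gives p = 0.025 on the FAS against 30% on placebo (about 39.3%), then retested with the excluded counted as failures.

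| eA / eP | Responder difference (points) | z, FAS → all dosed | Borderline p, from 0.025 | BOCF 70 mg (days) |
|---|---|---|---|---|
| 0.83% / 0.83% | 14.88 | 3.58 → 3.57 | 0.0253 | −1.091 |
| 1.67% / 1.67% | 14.75 | 3.56 → 3.54 | 0.0256 | −1.082 |
| 1.67% / 0.83% | 14.50 | 3.57 → 3.48 | 0.0304 | −1.067 |
| 0.83% / 1.67% | 15.13 | 3.57 → 3.63 | 0.0212 | −1.106 |
| 3% / 1% (stress) | 13.95 | 3.55 → 3.35 | 0.0392 | −1.031 |
| 1% / 3% (stress) | 15.45 | 3.56 → 3.71 | 0.0165 | −1.125 |

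In the first four rows the responder p-value with the excluded counted as failures is between 0.0003 and 0.0005; in the stress rows it is 0.0008 and 0.0002. With the planned SD of 4, the standard error of the 70 mg difference is 4 × √(2/330) = 0.31 day.

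**The case against.** SAP 2.2 sends the reader to Appendix 5.5, so Table 5-2 reads as the operational form of a general definition. SAP 2.5.4 describes the BOCF analysis as repeating the primary one, which SAP 2.5.1 places on the FAS, so the set can be inferred. The all-missing case is only an example of a rule that works otherwise. Set counts and a listing of patients excluded are already planned (SAP 2.3.1), and SAP 5.1.5.3 promises further analysis if missingness is high or unbalanced. The FAS-based responder analysis contradicts nothing.

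Most of this stands, and it rules out several stronger readings that a reader might infer:

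- That BOCF as a whole is void. It is not: patients with an earlier month and no Week 12 value are imputed.
- That two competing FAS sets are equally likely. The cross-reference makes Table 5-2 the natural choice.
- That no efficacy analysis anywhere includes these patients. Parts of the SAP are withheld, so this cannot be checked.
- That the primary result is biased by the rule. These patients give the observed-data mixed model no outcome under either wording.

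The objection does not answer one point. Following Table 5-2 as written takes the patients with least data out of the analyses meant to penalise missingness, and the promised further analysis names no set that would bring them back.

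**Conclusion.** The concern holds as a minor point. The two FAS wordings differ for one identifiable type of patient. On the Table 5-2 FAS the all-missing BOCF example is empty for migraine days. Non-responder imputation omits dosed patients with no evaluable month by explicit statement of the set; BOCF and multiple imputation omit them on the natural reading of SAP 2.5.1 with 2.5.4.

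Under the assumed 0.8% to 1.7% exclusion, BOCF moves by about 0.01 to 0.03 day against a standard error of 0.31, and the responder difference by 0.1 to 0.5 points. The stress cases reach 0.07 day and about 1 point. The direction depends on which arm loses more patients early. No conclusion changes unless the FAS result is already near its threshold. The exclusion rates, the arm splits and the 45% and 30% response rates are assumptions. The level of 0.025 in the borderline case is illustrative, because the updated testing figure is not in the public text.

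**What to change.** 1. Use one FAS rule, worded identically in SAP 2.2 and Table 5-2.
2. Keep the FAS for the observed-data mixed model.
3. Run the BOCF, MAR and control-based imputation analyses on all randomised and dosed patients with a baseline value, by randomised arm. One set for all three means that they differ only in the missing-data assumption. The MNAR steps in SAP 5.1.5.3.2 already build forward from baseline, and eligibility requires at least 80% baseline diary compliance, so nearly all dosed patients should qualify.
4. Analyse the 50% responder endpoint on the same set, at minimum as a named sensitivity analysis, and count patients with no evaluable month as non-responders.
5. Show the FAS exclusions by arm with reasons. This is a small extension of the counts and listings already planned.

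The cost is SAP wording, one population flag, a little programming, and slightly lower response rates.
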